**Table 1.1.2-2 Adverse events of quinine versus placebo for leg cramps (Cochrane analysis\*)**

Adverse event	Quinine	Placebo	Relative risk (95% CI)
Minor adverse events			
No. of individuals (16 studies)	725	722	
Any minor event	93 (12.8%)	68 (9.4%)	3% (0-6%)
Gastrointestinal symptoms	39 (5.4%)	16 (2.2%)	3% (1-5%)
Headache	36 (5.0%)	33 (4.6%)	NS
Tinnitus	10 (1.4%)	1 (0.1%)	NS
Pruritus, scaly rash	9 (1.2%)	3 (0.4%)	NS
Dizziness, drowsiness	8 (1.1%)	8 (1.1%)	NS
Myalgia, paresthesia	7 (1.0%)	10 (1.4%)	NS
Visual disturbance	4 (0.6%)	2 (0.3%)	NS
Fever	3 (0.4%)	1 (0.1%)	NS
Major adverse events			
No. of individuals (18 studies)	806	807	
Major event causing study stoppage	12 (1.5%)	11 (1.4%)	NS
Gastrointestinal symptoms	7 (0.9%)	1 (0.1%)	NS
Headache	2 (0.2%)	2 (0.2%)	NS
Tinnitus	1 (0.1%)	0 (0%)	NS
Pruritus, scaly rash	2 (0.2%)	0 (0%)	NS
Dizziness, drowsiness	3 (0.4%)	2 (0.2%)	NS
Myalgia, paresthesia	1 (0.1%)	0 (0%)	NS
Visual disturbance	0 (0%)	1 (0.2%)	NS
Fever	1 (0.1%)	0 (0%)	NS

[figure not shown]
\* Adapted from El-Tawil et al. [45]; NS – not significant.

This study will assess the safety of topical nasal quinine sulfate, dihydrate (6 mg daily) delivered via nasal atomizer and its ability to decrease the incident rate of confirmed SARS-CoV-2 infection. Sterile 0.9% saline will be provided as the placebo control.

## 1.2 Investigational Agent

GLS-1200 is used as the therapeutic agent in this study. GLS-1200 is formulated as a solution of quinine sulfate, dihydrate (Figure 1.2-1) USP dissolved into sterile normal saline (0.9% sodium chloride) at a concentration of 1 mg/ml and then filter sterilized. Quinine sulfate, dihydrate has a molecular weight of 782.94 g/mol.

Sterile normal saline (0.9% sodium chloride) will be used as the placebo solution in this study.

**Figure 1.2-1: Structure of Quinine sulfate, dihydrate**

### 1.3 Dose and Regimen Rationale

The dose of quinine sulfate, dihydrate used in this protocol (1 mg/ml) given three times per day via nasal atomizer is similar to that used by [Desrosiers et al.](#) [37] ([Table 1.1.2-1](#)). Subjects will continue three times daily quinine sulfate, dihydrate usage for 4 weeks. This length of time for quinine exposure is the same as that used by [Desrosier et al.](#) ([Table 1.1.2-1](#)). The quinine sulfate, dihydrate treatment regime in this protocol is similar to that used in another protocol (IND BB128711) that was reviewed and approved by the University of Pennsylvania IRB (Protocol # 821731).

### 1.4 Risk/Benefit Assessment

In accordance with the International Conference on Harmonization (ICH), this study has been designed to minimize the risk to study participants. Quinine treatment in this study does not replace or change everyday precautions taken by the study participants in preventing SARS-CoV-2 infection.

Quinine sulfate, dihydrate exposure in this study is 6 mg/day (1 ml of a 1 mg/ml solution used to irrigate each nostril, for total exposure of 2 mg per application, three times daily) and is similar to that used by [Desrosiers et al.](#) to study tobramycin vs saline placebo (where the placebo contained 1 mg/ml of quinine to mask taste) [37]. Doses ranging from 2.5 to 90 mg/day have been used as part of various studies for CF ([Table 1.1.2-1](#)). As reviewed above, the amount of quinine in an 8 oz. glass of tonic water is greater than 25 mg, while typical doses of quinine prescribed for leg cramps is 200-300 mg/day and for malaria is 1800 mg/day (600 mg three times daily).

The adverse effects of topical quinine are unknown. The adverse effects of orally prescribed quinine include hematologic changes (thrombocytopenia as most common and less commonly anemia) and electrocardiographic effects (particularly prolongation of the QTc). As reviewed, prior clinical studies of nasal or aerosol administered quinine in approximately 750 persons ([Table 1.1.2-1](#)) showed no quinine-associated adverse events.

The atomizer provided as part of this study is designed to provide a fine spray into the nose. There is the possibility that the atomizer will not function properly and will cause discomfort when used. Should this occur, study participants are asked to notify the study staff before their next dose. The study staff will discuss continued usage of the atomizer with the participant.

If the GLS-1200 or saline are accidentally sprayed into the eyes, ears or mouth, irritation may occur that could require evaluation. If the syringe and atomizer are not fully connected, the study participant may only receive a partial amount of study drug. If the atomizer or syringe packaging

is found to be open prior to use, it is possible that either component could be contaminated and thus there is a risk for infection. Devices with damaged packaging should not be used.

## **2. HYPOTHESIS AND STUDY OBJECTIVES**

### **2.1 Hypothesis**

GLS-1200 topical nasal spray administered Day 0 through Week 4 will be safe, well tolerated and reduce the incidence of confirmed SARS-CoV-2 infection.

### **2.2 Primary Objectives and Outcome Variables**

- Evaluate the safety and tolerability of GLS-1200 topical nasal spray
- Incidence of SARS-CoV-2 infection, confirmed by PCR relative to treatment group

### **2.3 Secondary Objectives and Outcome Variables**

- Symptom score of documented SARS-CoV-2 infection relative to treatment group

### **2.4 Exploratory Objectives**

- Incidence of SARS-CoV-2 seroconversion relative to treatment group
- Assess the relationship of taste receptor genetics to incidence of SARS-CoV-2 infection and relative to treatment group

## **3. STUDY DESIGN**

This is a Phase II, placebo-controlled, double-blind study of GLS-1200 topical nasal spray to assess the safety, tolerability, and ability to reduce the incidence of confirmed SARS-CoV-2 infection. Following recruitment and informed consent, those meeting enrollment criteria will be randomized 2:1 (GLS-1200:placebo). Participants will initiate topical nasal spray applications immediately after randomization and will continue for 4 weeks. Participants will self-administer drug three times daily. The primary outcome measurements are safety, tolerability, and reduction in the diagnosis of PCR-confirmed SARS-CoV-2 infection. Follow-up will continue through 6 weeks since some cases of SARS-CoV-2 infection may not be apparent until after the primary treatment period has concluded. Secondary measures will assess the incidence of symptoms between each visit, by treatment group. In addition the average number of days subjects experience each symptom will be summarized by treatment group. Exploratory measures will assess the incidence of seroconversion in serum and the relationship of taste receptor genetics to incidence of SARS-CoV-2 infection both relative to treatment group.

### **3.1 Safety Monitoring**

Subjects will be randomized in a blinded fashion to one of two study treatments (quinine or placebo) at fixed doses. Clinical adverse events (AEs) will be reviewed at each visit up to end of the study. Subjects will be requested to maintain a daily symptom diary to monitor for viral related symptoms and to assess any other potential adverse effects through 2 weeks of follow-up. Safety monitoring will also include laboratory assessment of hematology, chemistry and ECG performed at baseline (pre-treatment) and at Week 4 (end of treatment).

## **4. SELECTION AND ENROLLMENT OF PARTICIPANTS**

### **4.1 Recruitment of Participants**

Adult volunteers will be recruited for the current study.

---

#### **4.2 Inclusion Criteria**

1. Age 18 years or older
2. Able to provide informed consent
3. Able and willing to comply with study procedures
4. Able and willing to utilize an approved form of pregnancy prevention for women of child-bearing potential through to the end of treatment

#### **4.3 Exclusion Criteria**

1. Known allergy to quinine, quinidine or mefloquine
2. Confirmed prior positive test for SARS-CoV-2
3. Treatment within the past 2 weeks with chloroquine, hydroxychloroquine, or remdesivir
4. Pregnancy or documentation of pregnancy by pre-treatment urine pregnancy test or breast feeding or plans to become pregnant during the course of the study

#### **4.4 Discontinuation/Withdrawal of Study Participants**

Participants will be considered to have completed the study when he/she completes all scheduled study treatments and follow-up visits. If a participant discontinues the study at any time after enrollment, but prior to the final scheduled study visit, the investigator will make every effort to have the participant complete all assessments. At a minimum, study participants will be encouraged to complete all procedures included in the final study visit should they elect to terminate early. All data collected up to the time of early termination will be used for final analyses except as noted below. Categories of early termination are defined below:

- Voluntary withdrawal from the study: the participant verbalizes or states in writing their desire to withdraw from the study. Data already collected remains as part of the study.
- Lost to follow-up: the participant terminates, does/will not return to complete study visits and cannot be located, or does not respond to written or telephonic contact.
- Withdrawal of consent: the participant provides verbal or written request to withdraw from the study *and* also withdraws consent for use of study data. The investigator is encouraged to discuss withdrawal of consent to ensure that data collected up to the time of study withdrawal can be used for analysis.
- Protocol violation: the participant failed to adhere to protocol requirements. Such events will be discussed between the Medical Monitor and the site PI to determine whether these events constitute a deviation that requires removal of the participant from the study and/or non-use of study data.
- Adverse event (Adverse Reaction): clinical or laboratory events that in the medical judgement of the investigator are grounds for discontinuation for the best interest of the participant. This includes serious and non-serious adverse events regardless of relation to study drug.
- Death: the participant died.

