#### 6.1.4 Week 6: follow up visit

Study procedures that will be completed include:

- Review new concomitant medications
- Review adverse effects, any new diagnosis of SARS-CoV-2 infection

---

- Review and collect study diary
- Perform targeted physical exam
- Perform nasopharyngeal swab for viral PCR
- Collect serum for viral antibodies
- Collect and review diary

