**6.2.3.5 12-lead ECG**

A 12-lead ECG will be performed at enrollment and at the Week 4 visit.

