**6.2.3.6 Safety Laboratory Evaluations**

Blood draws for a complete blood count with differential and a basic metabolic panel (consisting of sodium, chloride, potassium, bicarbonate (CO2), blood urea nitrogen (BUN), creatinine, and glucose) will be performed at baseline and at the Week 4 visit.

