<Preferred Term #2>	x (xx.x%)	x (xx.x%)
<System Organ Class #2>	x (xx.x%)	x (xx.x%)
<Preferred Term #1>	x (xx.x%)	x (xx.x%)
<Preferred Term #2>	x (xx.x%)	x (xx.x%)
.	.	.
.	.	.

AE=adverse event; TEAE = Treatment-Emergent Adverse Event; MedDRA = Medical Dictionary for Regulatory Activities

AEs are coded using MedDRA version 23.0 and ordered by descending order of overall incidence of SOC and overall incidence of PT within each SOC. At each level of summation (overall, SOC, PT), subjects reporting more than one TEAE are counted only once.

Reference: Listing 16.2.7.3

Source: \\xx\\xxx\\xxx\\xxx\\xxxxxx\\xxxxxxxxxxxx\\xxxx\\xxxx.sas      date      time

Table 14.3.2.4  
Treatment-Emergent Adverse Events Leading to Death by System Organ Class and Preferred Term  
(Safety Population)

System Organ Class Preferred Term	GLS-1200 (N=XX)	Placebo (N=XX)
Subjects with at least one TEAE leading to death	x (xx.x%)	x (xx.x%)
<System Organ Class #1>	x (xx.x%)	x (xx.x%)
<Preferred Term #1>	x (xx.x%)	x (xx.x%)
<Preferred Term #2>	x (xx.x%)	x (xx.x%)
<System Organ Class #2>	x (xx.x%)	x (xx.x%)
<Preferred Term #1>	x (xx.x%)	x (xx.x%)
<Preferred Term #2>	x (xx.x%)	x (xx.x%)
.	.	.

AE=adverse event; TEAE = Treatment-Emergent Adverse Event; MedDRA = Medical Dictionary for Regulatory Activities

AEs are coded using MedDRA version 23.0 and ordered by descending order of overall incidence of SOC and overall incidence of PT within each SOC. At each level of summation (overall, SOC, PT), subjects reporting more than one TEAE are counted only once.

Reference: Listing 16.2.7.4

Source: \\xx\xxx\xxx\xxx\xxxxx\xxxxxxxxxxxxx\xxxx\xxxx.sas      date      time

Table 14.3.4.1  
Shift from Baseline in Hematology Results by Test and Visit  
(Safety Population)

Test	GLS-1200 (N=XX)			Placebo (N=XX)		
	Baseline	Low	Normal	High	Baseline	Normal
<Test #1> (units)						
Week 4						
n		x			x	
Low	xx (xx.x)	xx (xx.x)	xx (xx.x)	xx (xx.x)	xx (xx.x)	xx (xx.x)
Normal	xx (xx.x)	xx (xx.x)	xx (xx.x)	xx (xx.x)	xx (xx.x)	xx (xx.x)
High	xx (xx.x)	xx (xx.x)	xx (xx.x)	xx (xx.x)	xx (xx.x)	xx (xx.x)

Baseline is the last non-missing value prior to first dose of study treatment.

Percentages are based on n, the number of subjects with both a baseline and post-baseline result at the visit.

Shifts are based on local labs from each site.

Reference: Listing 16.2.8.1

Source: \\xx\xxx\xxx\xxx\xxxxx\xxxxxxxxxxxxx\xxxx\xxxx.sas      date      time

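### The minimum exit assessments are the Week 6 procedures, which omit ECG, CBC and chemistry, so participants who leave the study before Week 4 may have no scheduled post-baseline ECG or laboratory result

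*Protocol*

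**What the plan says.** Protocol 4.4 makes two requests about participants who leave early. The first is general: "the investigator will make every effort to have the participant complete all assessments". The second sets the floor, as a minimum: "study participants will be encouraged to complete all procedures included in the final study visit should they elect to terminate early". Section 4.4 lists adverse event among the categories of early termination.

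The final scheduled visit is Week 6. Protocol 6.1.4 lists concomitant medications, adverse effects and any new diagnosis, the diary, a targeted exam ("Perform targeted physical exam"), the swab and antibody serum. Protocol 6.2.3.3 adds vital signs at every visit. No ECG or safety laboratory test is listed.

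Those tests have their own sections. On the ECG, 6.2.3.5 says "A 12-lead ECG will be performed at enrollment and at the Week 4 visit". On the CBC and metabolic panel, 6.2.3.6 says they "will be performed at baseline and at the Week 4 visit". Table S2 agrees, and its Unscheduled column marks none of them.

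In SAP Appendix C, the footnote to the hematology shift table (14.3.4.1) reads "Percentages are based on n, the number of subjects with both a baseline and post-baseline result at the visit". The chemistry table repeats that layout and the ECG shift table carries the same rule. Week 4 is the only post-baseline row in each. SAP 9.4 applies the QTcF change categories to Week 4 only.

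**The concern.** Safety and tolerability are a primary objective (Protocol 2.2, SAP 2.1). Protocol 1.4 says the adverse effects of topical quinine are unknown. For orally prescribed quinine it names "hematologic changes (thrombocytopenia as most common and less commonly anemia) and electrocardiographic effects (particularly prolongation of the QTc"). A platelet count and a QTc come from the blood count and the ECG, and the minimum exit set has neither.

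The plan takes one post-baseline look at these measures. A participant who leaves before that look and does only the minimum contributes nothing to the tables that summarize them. If leaving is related to tolerability, those tables describe a selected group and could lean toward showing no effect. Grade 3 or greater laboratory abnormalities are also expedited events (7.3.1) that can count toward the stopping rules (7.3.2). An abnormality that is never measured cannot count.

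**Working it through.** The plan states no figure on this point, so there is none to reproduce. The check compares the exit rule with the schedule.

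**Step 1. What each visit contains** (Table S2, repeated as SAP Table 1)

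| Assessment | Day 0 | Week 2 | Week 4 | Week 6 | Unscheduled |
|---|---|---|---|---|---|
| 12-lead ECG | yes | no | yes | no | no |
| CBC with differential | yes | no | yes | no | no |
| Chemistry | yes | no | yes | no | no |
| Urine pregnancy test | yes | yes | yes | no | no |
| Adverse events | no | yes | yes | yes | yes |
| Exam and vital signs | yes | yes | yes | yes | yes |

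**Step 2. Apply the 4.4 minimum by time of exit**

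- Leaves the study before the Week 4 visit and completes the minimum: no scheduled ECG, CBC or chemistry after Day 0.
- Leaves between Weeks 4 and 6: the Week 4 tests have already fallen due.
- Stops the spray but stays in the study: the Week 4 tests are still scheduled.

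The gap is confined to the first group. Neither document defines an early-termination visit with its own tests. ET is in the SAP abbreviation list, but the SAP analysis sections do not use it.

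**Step 3. Follow that participant into the SAP tables**

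- Laboratory and ECG shift tables (14.3.4.1, 14.3.4.2, 14.3.4.4.1): excluded, because n requires a baseline and a post-baseline result and Week 4 is the only row.
- QTcF table (14.3.4.4.2): absent from the Week 4 categories, including change from baseline.
- Adverse event tables: still in the Safety Population denominator, with no scheduled test after baseline that could have shown a laboratory or ECG abnormality.

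**Step 4. Scale, for illustration only**

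Inputs: 150 on GLS-1200 (Table S1); a fraction *d* leaving before Week 4 and completing only the minimum, assumed to be 5%, 10% or 20%. Untested *m* = 150*d*, rounded; tested *n* = 150 − *m*. The exact two-sided 95% upper limit with zero events is 1 − 0.025^(1/*n*).

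| *d* | *m* | *n* | Upper limit, 0 events |
|---|---|---|---|
| 0 | 0 | 150 | 2.4% |
| 5% | 7.5, rounded to 8 | 142 | 2.6% |
| 10% | 15 | 135 | 2.7% |
| 20% | 30 | 120 | 3.0% |

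Little precision is lost. To see the effect of selection, assume an abnormality rate of 1% in completers and 10% in early leavers. The overall rate is then (1 − *d*) × 1% + *d* × 10%:

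- *d* = 5%: 0.95% + 0.5% = 1.45%
- *d* = 10%: 0.9% + 1.0% = 1.9%
- *d* = 20%: 0.8% + 2.0% = 2.8%

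The Week 4 table would show about 1% in each case. The 1% and 10% are assumptions chosen to show direction. They do not come from the documents.

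**The case against.** The best reply is that 4.4 already asks for every effort to complete all assessments, so the Week 6 set is a floor and not the whole request. That stands, and it rules out saying that early leavers will have no tests. It does not close the gap, because the general sentence names no tests and no timing, while the only concrete instruction points to the visit without them.

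A reader might go on to infer several stronger things that the documents do not support:

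- *That these participants have no safety assessment at all.* The Week 6 set keeps the adverse event query, vital signs and a targeted exam. Nothing bars testing for cause: Protocol 7.1.6 refers to abnormalities that need diagnostic tests, and 9.6 covers events found by laboratory test.
- *That an exit result would have nowhere to go, or that the reports would show zero.* SAP 9.2 lists all laboratory parameters and 9.4 has an ECG listing. A new or worsened laboratory abnormality that is clinically significant, or that leads to stopping treatment, is recorded as an adverse event under Protocol 7.1.6. SAP 9.2 and 9.4 speak of each post-baseline visit, and Appendices A and B let the layouts be reorganized. The gap in reporting is limited to the shift tables and the QTcF summary.
- *That early leavers are those most likely to have had toxicity.* Section 4.4 also lists voluntary withdrawal, loss to follow-up and protocol violation. The link to toxicity is plausible but is not stated.
- *That hematologic and QTc effects are known risks of this product.* Section 1.4 ties them to oral quinine. It gives 6 mg/day for this trial against 200-300 mg/day for leg cramps and 1800 mg/day for malaria, and reports no quinine-associated events in about 750 nasal or aerosol recipients.

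**Conclusion.** The point holds in a limited form. The stated minimum for early termination points to a visit without ECG, CBC or chemistry, although safety is a primary objective and the plan takes only one post-baseline look at those measures. Participants who leave the study before Week 4 and complete only the minimum have no scheduled post-baseline result and fall out of the laboratory and ECG shift tables and the QTcF-change summary.

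The missingness may be informative, because adverse event is a named reason for leaving. Its size cannot be known from the documents, which give no dropout rate. The 8, 15 or 30 untested participants on GLS-1200 are upper figures for the assumed 5%, 10% and 20%: they take every exit as falling before Week 4 and nobody as doing more than the minimum. The issue is selection more than precision. The text of both documents establishes the gap with high confidence; how much it would matter is uncertain. It should be corrected, but it does not undermine the design.

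**What to change.** **Protocol.** Reconcile 4.4 with Table S2. State that for exits before Week 4 the minimum set includes the safety assessments already scheduled at Week 4: 12-lead ECG, CBC with differential, chemistry and urine pregnancy test. Mark them in an early-termination column of Table S2. The Week 4 list already has the adverse event and diary review, so nothing more is needed for those.

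**SAP.** In 9.2 and 9.4, and in Tables 14.3.4.1, 14.3.4.2, 14.3.4.4.1 and 14.3.4.4.2, add a last post-baseline row that includes early-termination results, beside the Week 4 row. Report by arm how many participants have no post-baseline result, so that the reader can see how selected each table is.

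**Cost.** One sentence in 4.4, one column in Table S2 and one row per SAP table. The tests are ones that every participant is already scheduled to have at Week 4. The downside is a longer exit visit. Participants who are lost to follow-up or refuse the visit will still be missing.

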### **5. STUDY PRODUCT**

#### **5.1 Investigational Product**

GLS-1200, containing quinine sulfate, dihydrate, USP, the investigational product used in this study, is a small molecule with a chemical structure as shown in [Figure 1.2-1](#). Quinine sulfate, dihydrate, USP will be formulated in 0.9% sterile saline at 1 mg/ml, filter sterilized and provided

to participants in vials with 7.0 ml recoverable volume for daily use. Quinine has been shown to be stable in neutral, weak and strong acid solutions, and weak base solutions, without light exposure for up to 285 days [47]. In contrast, when ultraviolet exposure occurs, the solution's pH influences the rate of decrease in the concentration of quinine: rapid loss in 0.0005N NaOH; much slower decreases in water or strong acids; and the slowest loss in weak solutions of 0.03N HCl [47]. The quinine solution is approximately pH 6 for this study.

Sterile, 0.9% sodium chloride (normal saline), will be used as the placebo solution. Sterile saline will be provided in vials with 7.0 ml recoverable volume for daily use.

## 5.2 Packaging and Labeling

Study product will be supplied in kits labeled only with a randomly generated Treatment Kit #. Each kit will contain 28 vials of study drug (sufficient for 28 days of treatment) with each vial containing 7 mL of study drug. Study product will be stored at the University of Pennsylvania Investigational Drug Service. Vials of drug will be provided packaged in a cardboard box and inside amber plastic bags to reduce UV exposure.

Drug product labels are shown below in **Table 5.2-1**. Labels are generated in tandem as shown: one side to be affixed to each Drug Product kit and the second side as detachable for pharmacy logs. As participants present for randomization, treatment assignments will follow the randomization schema in successive order. The study pharmacist will write the Subject ID# and dispensing date on the two labels at the time of study drug dispensation. The side that had been affixed to the Drug Product Kit will remain, while the other half is detached and affixed into the Pharmacy Log form. As noted, the detachable side for Pharmacy is designated as to whether the vials in the kit contain active drug (GLS-1200) or placebo (0.9% saline).

The randomized Treatment Kit # and the designation as Active or Placebo serve as independent confirmatory checks on treatment assignment.

